
Grade 2      Hold study drug/study regimen dose until Grade 2 resolution to Grade <math>\leq 1</math>.
 
If toxicity worsens, then treat as Grade 3 or Grade 4.
 
Study drug/study regimen can be resumed once event stabilizes to Grade <math>\leq 1</math> after completion of steroid taper.
 
Patients with endocrinopathies who may require prolonged or continued steroid replacement can be retreated with study drug/study regimen on the following conditions:
 
 
1. The event stabilizes and is controlled.
 
2. The patient is clinically stable as per Investigator or treating physician's clinical judgement.
 
3. Doses of prednisone are at <math>\leq 10</math> mg/day or equivalent.
 
	

Grade 3      Depending on the individual toxicity, study drug/study regimen may be permanently discontinued. Please refer to guidelines below.
 
Grade 4      Permanently discontinue study drug/study regimen.
 
Note: For asymptomatic amylase or lipase levels of <math>>2.0 \times</math>ULN, hold study drug/study regimen, and if complete work up shows no evidence of pancreatitis,
	

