**NU Study Number: NU 15B01**  
**Other Study Number: MedImmune # ESR-14-10694 (D4190C00030)**

---

>3.0×baseline if baseline abnormal
 
 
≤3.0×baseline and/or TB ≤1.5×baseline if baseline abnormal
 
• Resume study drug/study regimen if elevations downgrade to AST or ALT ≤3.0×ULN and/or TB ≤1.5×ULN if baseline normal, or to AST or ALT ≤3.0×baseline and/or TB ≤1.5×baseline if baseline abnormal, within 14 days and after completion of steroid taper.           
 
• Permanently discontinue study drug/study regimen if the elevations do not downgrade as described in bullet above within 14 days
 
 
 
 
For elevations in transaminases >8×ULN or elevations in TB >5×ULN if baseline normal, or for elevations in transaminases >8×baseline and/or TB >5×baseline if baseline abnormal, permanently discontinue study drug/study regimen.
 
Permanently discontinue study drug/study regimen for any case meeting Hy's law criteria (AST and/or ALT >3 × ULN + bilirubin >2 × ULN without initial findings of cholestasis (i.e., elevated alkaline P04) and in the absence of any alternative cause.b
	
Once the patient is improving, gradually taper steroids over ≥28 days and consider prophylactic antibiotics, antifungals, and anti-PJP treatment (refer to current NCCN guidelines for treatment of cancer-related infections).a

---	--

---

---

Nephritis or renal dysfunction	Any Grade	General Guidance	For Any Grade:
(elevated serum creatinine)			

– Consult with nephrologist.

– Monitor for signs and symptoms that may be related to changes in renal function (e.g., routine urinalysis, elevated serum BUN and creatinine, decreased creatinine clearance, electrolyte imbalance, decrease in urine output, or proteinuria).

– Patients should be thoroughly evaluated to rule out any alternative etiology (e.g., disease progression or infections).

– Steroids should be considered in the absence of clear alternative etiology even for low-grade events (Grade 2), in order to prevent potential progression to higher grade event.

---

---

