
Grade 1  (Serum creatinine > 1 to <math>1.5 \times</math>baseline; > ULN to <math>1.5 \times</math>ULN)
	
No dose modifications.
	
For Grade 1:
 
 
– Monitor serum creatinine weekly and any accompanying symptoms. 
 
• If creatinine returns to baseline, resume its regular monitoring per study protocol.
 
• If creatinine worsens, depending on the severity, treat as Grade 2, 3, or 4.
 
 
 
– Consider symptomatic treatment, including hydration, electrolyte replacement, and diuretics.
 

Grade 2  (serum creatinine >1.5 to <math>3.0 \times</math>baseline; >1.5 to <math>3.0 \times</math>ULN)
	
Hold study drug/study regimen until resolution to Grade <math>\leq 1</math> or baseline.
 
 
• If toxicity worsens, then treat as Grade 3 or 4.
 
• If toxicity improves to Grade <math>\leq 1</math> or baseline, then resume study drug/study regimen after completion of steroid taper.
 
	
For Grade 2:
 
 
– Consider symptomatic treatment, including hydration, electrolyte replacement, and diuretics.
 
– Carefully monitor serum creatinine every 2 to 3 days and as clinically warranted.
 
– Consult nephrologist and consider renal biopsy if clinically indicated.
 
– If event is persistent (<math>>3</math> to 5 days) or worsens, promptly start prednisone 1 to 2 mg/kg/day PO or IV equivalent.
 
– If event is not responsive within 3 to 5 days or worsens despite prednisone at 1 to 2 mg/kg/day PO or IV equivalent, additional workup should be considered and prompt treatment with IV methylprednisolone at 2 to 4 mg/kg/day started.
 
– Once the patient is improving, gradually taper steroids over <math>\geq 28</math> days and consider prophylactic antibiotics, antifungals, and anti-PJP treatment (refer to current NCCN guidelines for treatment of cancer-related infections).a
 
– When event returns to baseline, resume study drug/study regimen and routine serum creatinine monitoring per study protocol.
 

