**Prohibited concomitant medications**

Prohibited medication/class of drug:	Usage:
Any investigational anticancer therapy other than those under investigation in this study	Should not be given concomitantly whilst the patient is on study treatment
mAbs against CTLA-4, PD-1, or PD-L1 other than those under investigation in this study	Should not be given concomitantly whilst the patient is on study treatment
Any concurrent chemotherapy, radiotherapy, immunotherapy, or biologic or hormonal therapy for cancer treatment other than those under investigation in this study	Should not be given concomitantly whilst the patient is on study treatment. (Concurrent use of hormones for non-cancer-related conditions [eg, insulin for diabetes and hormone replacement therapy] is acceptable. Local treatment of isolated lesions, excluding target lesions, for palliative intent is acceptable [eg, by local surgery or radiotherapy])
Immunosuppressive medications including, but not limited to, systemic corticosteroids at doses exceeding 10 mg/day of prednisone or equivalent, methotrexate, azathioprine, and tumor necrosis factor- $\alpha$ blockers	
Should not be given concomitantly, or used for premedication prior to the I-O infusions. The following are allowed exceptions:
 
 
• Use of immunosuppressive medications for the management of IP-related AEs,
 
• short-term premedication for patients receiving combination agent where the prescribing information for the agent requires the use of steroids for documented hypersensitivity reactions
 
• Use in patients with contrast allergies.
 
• In addition, use of inhaled, topical, and intranasal corticosteroids is permitted.
 
 
A temporary period of steroids will be allowed if clinically indicated and considered to be essential for the management of the patient (eg, chronic obstructive pulmonary disease, radiation, nausea, etc).

Drugs with laxative properties and herbal or natural remedies for constipation	Should be used with caution through to 90 days after the last dose of tremelimumab during the study
Sunitinib	Should not be given concomitantly or through 90 days after the last dose of tremelimumab (acute renal failure has been reported with combination therapy of tremelimumab and sunitinib)

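### Section 4.3, Grade 2 nephritis: one Toxicity Management bullet restarts study drug without the steroid-taper condition that the same row's dosing cell imposes

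*Combined protocol and SAP*

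**What the plan says.** All the text at issue is current. It stands in the guideline tables of Section 4.3, dated 17 October 2019.

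- **Grade 2 nephritis, Dose Modifications cell.** Drug is held until creatinine is back to Grade 1 or lower, or to baseline. The restart clause ends "or baseline, then resume study drug/study regimen after completion of steroid taper".
- **General Considerations, Grade 2.** "Study drug/study regimen can be resumed once event stabilizes to Grade" 1 or lower, and the sentence goes on to require a finished taper. The exception written there is for hormone-related events: "Patients with endocrinopathies who may require prolonged or continued steroid replacement can be retreated with study drug/study regimen on the following conditions". Those conditions are a stable, controlled event, a clinically stable patient, and prednisone of no more than 10 mg/day.
- **Grade 2 nephritis, Toxicity Management, second-to-last bullet.** "Once the patient is improving, gradually taper steroids over" at least 28 days.
- **Same cell, last bullet.** "When event returns to baseline, resume study drug/study regimen and routine serum creatinine monitoring per study protocol".

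Steroids are a foreseeable part of this pathway. The row starts prednisone at 1 to 2 mg/kg/day if the event lasts beyond 3 to 5 days or worsens, and the any-grade nephritis guidance asks physicians to consider steroids for Grade 2 events.

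**The concern.** A restart rule should give one answer on a given day. Here a physician reading across the row finds two. For a patient whose creatinine has normalised but who is still tapering, the dosing cell says to keep holding and the last bullet says to resume. The bullet names the study drug, so it is a dosing instruction and not just a comment on monitoring.

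What is at stake is consistent and safe re-dosing after an immune-mediated kidney event. Section 11.7 requires the study to be run exactly as the protocol describes, so two answers also make it unclear which restart would be a deviation.

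**Working it through.** The plan gives no figure to reproduce. The check compares wording and then bounds the time between the two restart dates.

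**1. The three restart texts**

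| Text | Creatinine condition | Taper finished? |
|---|---|---|
| Grade 2 nephritis, Dose Modifications | Grade 1 or lower, or baseline | Required |
| General Grade 2 rule | Grade 1 or lower | Required |
| Grade 2 nephritis, last Toxicity Management bullet | Baseline | Not mentioned |

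**2. Can the texts point different ways for a real patient?** Yes. The taper begins on improvement, not on recovery, and runs for at least 28 days. Creatinine can therefore reach baseline before it ends.

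**3. Does another rule close the gap?** The prohibited-medication table in Section 4.4 limits systemic steroids, but among its exceptions is "Use of immunosuppressive medications for the management of IP-related AEs". It therefore does not prevent dosing during a treatment taper.

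**4. Size of the gap.** Let T be the taper length and d the days from the start of the taper to return to baseline. The bullet's restart date precedes the end of the taper by

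G = max(0, T − d).

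T = 28 is the row's minimum. The values of d are assumptions, because the documents give no recovery times. They also assume that the taper has started by the time baseline is reached. The number of scheduled doses falling inside the gap lies between floor(G/I) and ceil(G/I), where I is the dosing interval in Section 4.2 (28 days in the combination phase, 14 days in maintenance) and the visit calendar is assumed unchanged.

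| d (days) | G = 28 − d (days) | Four-weekly doses in gap | Two-weekly doses in gap |
|---|---|---|---|
| 0 | 28 | 1 | 2 |
| 7 | 21 | 0–1 | 1–2 |
| 14 | 14 | 0–1 | 1 |
| 21 | 7 | 0–1 | 0–1 |
| 28 | 0 | 0 | 0 |

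A taper longer than 28 days adds up to one day of gap per extra day. With no steroids there is no taper and G = 0.

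**5. The second mismatch runs the other way.** The row puts Grade 1 at creatinine up to 1.5 times baseline or up to 1.5 times the upper limit of normal. A patient who settles there, off steroids, may restart under the dosing cell but has not met the bullet's condition. The documents give nothing from which to size this delay.

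**The case against.** The best case against the point is that the row already answers the question. The dosing cell is explicit and the general rule agrees with it. General Considerations says that drug modifications will be made, whereas it only recommends the toxicity management steps. The bullet comes straight after the taper bullet, so the list can be read in clinical order: treat, taper, then restart. Its closing reference to the study protocol could send the reader back to the dosing rule. A physician who waits for both the end of the taper and baseline satisfies every text. Nephrology consultation is listed for any grade and again for Grade 2, so a restart on one isolated line is unlikely.

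Most of this stands, and it is why severity is low. It does not remove the conflict. No sentence says which column prevails, nothing in the list says that the taper must end before the last step, and the bullet itself orders a restart.

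Three stronger readings are tempting and are not supported.

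- A reader might infer that patients would be re-dosed on full treatment doses of prednisone, far above the 10 mg/day in the general rule. The 1 to 2 mg/kg/day dose applies before tapering. The dose remaining at restart is not given, and the 10 mg/day figure belongs to the exception for endocrine steroid replacement.
- A reader might take the Grade 1 bullet, "If creatinine returns to baseline, resume its regular monitoring per study protocol", as proof that the Grade 2 reference to the protocol covers monitoring only. No drug is held at Grade 1, so that bullet had no restart to mention and settles nothing.
- A reader might see a wider pattern, because the Grade 2 rows for peripheral neuromotor syndromes and myositis state no taper condition. Those rows are silent on the taper; they do not contradict themselves.

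**Conclusion.** The point holds as an internal inconsistency of low severity. Two instructions in one row give different restart conditions, and the looser one on steroids, read literally, allows dosing during a taper that the other makes a reason to hold. For the minimum taper the early restart is 0 to 28 days. The 28-day end requires baseline on the first day of the taper, so it is a bound and not an expected value. Under an unchanged calendar this covers at most one combination dose or two maintenance doses.

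The documents give no Grade 2 nephritis rate for this regimen, so the number of patients affected cannot be stated. Nor do they contain data showing that restarting during a taper brings the nephritis back, so no harm rate can be claimed. Overall response rate, sample size and the planned analyses do not depend on this wording.

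**What to change.** Remove the study drug from the last bullet, so that it says only that routine serum creatinine monitoring resumes once the event is back to baseline. The Dose Modifications cell then becomes the row's only restart rule, and both mismatches disappear. Adding a taper condition to the bullet would be weaker, because its baseline requirement would still differ from the cell's Grade 1 or lower, or baseline.

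The cost is one line of text, with no extra visits, patients or analyses. The change departs from the drug supplier's dated guideline wording and needs an amendment with the reviews listed in Section 11.2. The benefit is limited. Appendix E (Amendment 12) records that the study closed on 7.20.2020 for low accrual. Section 4.1.2 allows up to 52 further weeks of durvalumab, so dosing after closure was possible, but the documents do not say whether anyone remained on drug. Otherwise the correction helps a later study that reuses this table.

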**Grade 3 or 4**

**For Grade 3:**

Hold study drug/study regimen dose until resolution to Grade  $\leq 1$ .

Permanently discontinue study drug/study regimen if Grade 3 imAE does not resolve to Grade  $\leq 1$  within 30 days or if there are signs of respiratory insufficiency or autonomic instability.

**For Grade 4:**

Permanently discontinue study drug/study regimen.

**For Grade 3 or 4 (severe or life-threatening events):**

- Consider, as necessary, discussing with study physician.
  - Recommend hospitalization.
- Monitor symptoms and obtain Neurology consult.

*MYASTHENIA GRAVIS:*

- Steroids may be successfully used to treat myasthenia gravis. They should typically be administered in a monitored setting under supervision of a consulting neurologist.
- Patients unable to tolerate steroids may be candidates for treatment with plasmapheresis or IV IG.
- If myasthenia gravis-like neurotoxicity present, consider starting AChE inhibitor therapy in addition to steroids. Such therapy, if successful, can also serve to reinforce the diagnosis.

*GUILLAIN-BARRE:*

- It is important to consider here that the use of steroids as the primary treatment of Guillain-Barre is not typically considered effective.
- Patients requiring treatment should be started with IV IG and followed by plasmapheresis if not responsive to IV IG.

Myocarditis	Any Grade	General Guidance	For Any Grade:
		
Discontinue drug permanently if biopsy-proven immune-mediated myocarditis.
	
 
– The prompt diagnosis of immune-mediated myocarditis is important, particularly in patients with baseline cardiopulmonary disease and reduced cardiac function.
 
– Consider, as necessary, discussing with the study physician.
 
– Monitor patients for signs and symptoms of myocarditis (new onset or worsening chest pain, arrhythmia, shortness of breath, peripheral edema). As some symptoms can overlap with lung toxicities, simultaneously evaluate for and rule out pulmonary toxicity as well as other causes (e.g., pulmonary embolism, congestive heart failure, malignant pericardial effusion). A Cardiology consultation should be obtained early, with prompt assessment of whether and when to complete a cardiac biopsy, including any other diagnostic procedures.
 
– Initial work-up should include clinical evaluation, BNP, cardiac enzymes, ECG, echocardiogram (ECHO), monitoring of oxygenation via pulse oximetry (resting and exertion), and additional laboratory work-up as indicated. Spiral CT or cardiac MRI can complement ECHO to assess wall motion abnormalities when needed.
 
– Patients should be thoroughly evaluated to rule out any alternative etiology (e.g., disease progression, other medications, or infections)
 

	Grade 1	
No dose modifications required unless clinical suspicion is high, in which case hold study drug/study regimen dose during diagnostic work-up for other etiologies. If study drug/study regimen is held, resume after complete resolution to Grade 0.
	
For Grade 1 (no definitive findings):
 
 
– Monitor and closely follow up in 2 to 4 days for clinical symptoms, BNP, cardiac enzymes, ECG, ECHO, pulse oximetry (resting and exertion), and laboratory work-up as clinically indicated.
 
– Consider using steroids if clinical suspicion is high.
 

Grade 2, 3 or 4
 
(Grade 2: Symptoms with mild to moderate activity or exertion)
 
(Grade 3: Severe with symptoms at rest or with minimal activity or exertion; intervention indicated)
 
(Grade 4: Life-threatening consequences; urgent intervention indicated (e.g., continuous IV therapy or mechanical hemodynamic support))
	
 
- If Grade 2 -- Hold study drug/study regimen dose until resolution to Grade 0. If toxicity rapidly improves to Grade 0, then the decision to reinitiate study drug/study regimen will be based upon treating physician's clinical judgment and after completion of steroid taper. If toxicity does not rapidly improve, permanently discontinue study drug/study regimen.
 
 
If Grade 3-4, permanently discontinue study drug/study regimen.
	
For Grade 2-4:
 
 
- Monitor symptoms daily, hospitalize.
 
- Promptly start IV methylprednisolone 2 to 4 mg/kg/day or equivalent after Cardiology consultation has determined whether and when to complete diagnostic procedures including a cardiac biopsy.
 
- Supportive care (e.g., oxygen).
 
- If no improvement within 3 to 5 days despite IV methylprednisolone at 2 to 4 mg/kg/day, promptly start immunosuppressive therapy such as TNF inhibitors (e.g., infliximab at 5 mg/kg every 2 weeks). Caution: It is important to rule out sepsis and refer to infliximab label for general guidance before using infliximab.
 
- Once the patient is improving, gradually taper steroids over <math>\geq 28</math> days and consider prophylactic antibiotics, antifungals, or anti-PJP treatment (refer to current NCCN guidelines for treatment of cancer-related infections).a
 

--	---	--

Myositis/Polymyositis ("Poly/myositis")	Any Grade	General Guidance	For Any Grade:
			
 
- Monitor patients for signs and symptoms of poly/myositis. Typically, muscle weakness/pain occurs in proximal muscles including upper arms, thighs, shoulders, hips, neck and back, but rarely affects the extremities including hands and fingers; also difficulty breathing and/or trouble swallowing can occur and progress rapidly. Increased general feelings of tiredness and fatigue may occur, and there can be new-onset falling, difficulty getting up from a fall, and trouble climbing stairs, standing up from a seated position, and/or reaching up.
 
- If poly/myositis is suspected, a Neurology consultation should be obtained early, with prompt guidance on diagnostic procedures. Myocarditis may co-occur with poly/myositis; refer to guidance under Myocarditis. Given breathing complications, refer to guidance under Pneumonitis/ILD. Given possibility of an existent (but previously unknown) autoimmune disorder, consider Rheumatology consultation.
 

- Consider, as necessary, discussing with the study physician.
- Initial work-up should include clinical evaluation, creatine kinase, aldolase, LDH, BUN/creatinine, erythrocyte sedimentation rate or C-reactive protein level, urine myoglobin, and additional laboratory work-up as indicated, including a number of possible rheumatological/antibody tests (i.e., consider whether a rheumatologist consultation is indicated and could guide need for rheumatoid factor, antinuclear antibody, anti-smooth muscle, antisynthetase [such as anti-Jo-1], and/or signal-recognition particle antibodies). Confirmatory testing may include electromyography, nerve conduction studies, MRI of the muscles, and/or a muscle biopsy. Consider Barium swallow for evaluation of dysphagia or dysphonia.

Patients should be thoroughly evaluated to rule out any alternative etiology (e.g., disease progression, other medications, or infections).

Grade 1  (mild pain)	

- No dose modifications.

	For Grade 1: 

– Monitor and closely follow up in 2 to 4 days for clinical symptoms and initiate evaluation as clinically indicated.

– Consider Neurology consult.

– Consider, as necessary, discussing with the study physician.

Grade 2  (moderate pain associated with weakness; pain limiting instrumental activities of daily living [ADLs])	
Hold study drug/study regimen dose until resolution to Grade <math>\leq 1</math>.
 

- Permanently discontinue study drug/study regimen if it does not resolve to Grade <math>\leq 1</math> within 30 days or if there are signs of respiratory insufficiency.

	For Grade 2: 

– Monitor symptoms daily and consider hospitalization.

– Obtain Neurology consult, and initiate evaluation.

– Consider, as necessary, discussing with the study physician.

– If clinical course is rapidly progressive (particularly if difficulty breathing and/or trouble swallowing), promptly start IV methylprednisolone 2 to 4 mg/kg/day systemic steroids along with receiving input from Neurology consultant

– If clinical course is not rapidly progressive, start systemic steroids (e.g., prednisone 1 to 2 mg/kg/day PO or IV equivalent); if no improvement within 3 to 5 days, continue additional work up and start treatment with IV methylprednisolone 2 to 4 mg/kg/day

– If after start of IV methylprednisolone at 2 to 4 mg/kg/day there is no improvement within 3 to 5 days, consider start of immunosuppressive therapy such as TNF inhibitors (e.g., infliximab at 5 mg/kg every 2 weeks). Caution: It is important to rule out sepsis and refer to infliximab label for general guidance before using infliximab.

- Once the patient is improving, gradually taper steroids over  $\geq 28$  days and consider prophylactic antibiotics, antifungals, or anti-PJP treatment (refer to current NCCN guidelines for treatment of cancer-related infections).a


Grade 3 or 4            (pain associated with severe weakness; limiting self-care ADLs)
	
For Grade 3:            Hold study drug/study regimen dose until resolution to Grade <math>\leq 1</math>.
 
Permanently discontinue study drug/study regimen if Grade 3 imAE does not resolve to Grade <math>\leq 1</math> within 30 days or if there are signs of respiratory insufficiency.
 
For Grade 4:
 
 
- Permanently discontinue study drug/study regimen.
 
	
For Grade 3 or 4 (severe or life-threatening events):
 
 
– Monitor symptoms closely; recommend hospitalization.
 
– Obtain Neurology consult, and complete full evaluation.
 
– Consider, as necessary, discussing with the study physician.
 
– Promptly start IV methylprednisolone 2 to 4 mg/kg/day systemic steroids along with receiving input from Neurology consultant.
 
– If after start of IV methylprednisolone at 2 to 4 mg/kg/day there is no improvement within 3 to 5 days, consider start of immunosuppressive therapy such as TNF inhibitors (e.g., infliximab at 5 mg/kg every 2 weeks). Caution: It is important to rule out sepsis and refer to infliximab label for general guidance before using infliximab.
 
– Consider whether patient may require IV IG, plasmapheresis.
 
– Once the patient is improving, gradually taper steroids over <math>\geq 28</math> days and consider prophylactic antibiotics, antifungals, or anti-PJP treatment (refer to current NCCN guidelines for treatment of cancer-related infections).a
 

---	---	--

aASCOEdu  
cational  
Book  
2015  
“Manag  
ing Immune  
Checkpoi  
nt  
Blocking  
Antibody  
Side  
Effects”  
by  
Michael  
Postow  
MD.  
bFDA  
Liver  
Guidance  
Document  
2009  
Guidance  
for  
Industry:  
Drug  
Induced

Liver Injury – Premarketing Clinical Evaluation.

AChE Acetylcholine esterase; ADL Activities of daily living; AE Adverse event; ALP Alkaline phosphatase test; ALT Alanine aminotransferase; AST Aspartate aminotransferase; BUN Blood urea nitrogen; CT Computed tomography; CTCAE Common Terminology Criteria for Adverse Events; ILD Interstitial lung disease; imAE immune-mediated adverse event; IgG Immunoglobulin; IV Intravenous; GI Gastrointestinal; LFT Liver function tests; LLN Lower limit of normal; MRI Magnetic resonance imaging; NCI National Cancer Institute; NCCN National Comprehensive Cancer Network; PJP *Pneumocystis jirovecii* pneumonia (formerly known as *Pneumocystis carinii* pneumonia); PO By mouth; T3 Triiodothyronine; T4 Thyroxine; TB Total bilirubin; TNF Tumor necrosis factor; TSH Thyroid-stimulating hormone; ULN Upper limit of normal.

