## Dosing Modification and Toxicity Management Guidelines for Immune-Mediated, Infusion-Related, and Non-Immune-Mediated Reactions (MEDI4736 Monotherapy or Combination Therapy With Tremelimumab or Tremelimumab Monotherapy) 17 October 2019 Version (CTCAE v4.03)

### General Considerations regarding Immune-Mediated Reactions

Dose Modifications	Toxicity Management

study drug/study regimen may be continued or resumed.
 
Note: Study drug/study regimen should be permanently discontinued in Grade 3 events with high likelihood for morbidity and/or mortality – e.g., myocarditis, or other similar events even if they are not currently noted in the guidelines.
 
Similarly, consider whether study drug/study regimen should be permanently discontinued in Grade 2 events with high likelihood for morbidity and/or mortality – e.g., myocarditis, or other similar events even if they are not currently noted in the guidelines – when they do not rapidly improve to Grade <1 upon treatment with systemic steroids and following full taper
 
Note: There are some exceptions to permanent discontinuation of study drug for Grade 4 events (i.e., hyperthyroidism, hypothyroidism, Type 1 diabetes mellitus).
	

With long-term steroid and other immunosuppressive use, consider need for Pneumocystis jirovecii pneumonia (PJP, formerly known as Pneumocystis carinii pneumonia) prophylaxis, gastrointestinal protection, and glucose monitoring.

Discontinuation of study drug/study regimen is not mandated for Grade 3/Grade 4 inflammatory reactions attributed to local tumor response (e.g., inflammatory reaction at sites of metastatic disease and lymph nodes). Continuation of study drug/study regimen in this situation should be based upon a benefit-risk analysis for that patient.

AE Adverse event; CTC Common Toxicity Criteria; CTCAE Common Terminology Criteria for Adverse Events; imAE immune-mediated adverse event; IV intravenous; NCI National Cancer Institute; PO By mouth.

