#### **Myocarditis**

Across the durvalumab monotherapy pool of studies, as of the DCO of 12 July 2017 there has been 1 serious report of CTC Grade 3 myocarditis and 2 additional cases (Grade 3 and Grade 4) outside of the pooled dataset. In all cases the patients recovered or were improving with corticosteroid therapy.

Across the durvalumab plus tremelimumab combination pool of studies as of 12 July 2017 there has been 1 report of myocarditis. In addition myocarditis has been reported in 4 patients from clinical studies outside of the pooled dataset: 3 patients receiving durvalumab plus tremelimumab (1 of which resulted in a fatal outcome not considered related by the Investigator) and 1 patient receiving durvalumab plus tremelimumab in combination with cytotoxic chemotherapy agents, etoposide and carboplatin (which resulted in a fatal outcome).

Investigators should be aware of such rare, but severe immune-mediated adverse events including myocarditis with its presenting signs/symptoms (eg, decreased ejection fraction, arrhythmias, in particular occurrences of atrioventricular block).

For patients with suspected myocarditis, investigators should obtain a cardiology consult and institute full diagnostic work-up (that includes exclusion of other alternate causes such as infection) and the appropriate management that includes discontinuing drug (permanently if event progresses to Grade 3 or 4) and the prompt use of steroids or other immunosuppressives.

For rapid recovery of Grade 1 and 2 events, re-expose with treatment is possible. Patients with pre-existing cardiac disorders should be closely monitored for deterioration in their cardiac condition, which could suggest new onset myocarditis.

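### Section 7.2.5 allows re-exposure after rapid recovery from Grade 1–2 myocarditis without the biopsy-proven exception that the Section 4.3 toxicity table imposes at any grade

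*Combined protocol and SAP*

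**What the plan says.** Two parts of the protocol tell the investigator what to do with study drug in myocarditis.

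**Section 4.3, toxicity guideline (17 October 2019 version), Myocarditis.**
- Any grade: "Discontinue drug permanently if biopsy-proven immune-mediated myocarditis".
- Grade 1, which the table describes as having nothing definitive: no modification unless suspicion is high. Otherwise, "If study drug/study regimen is held, resume after complete resolution to Grade 0".
- Grade 2: hold until Grade 0. For restarting, the row says: "If toxicity rapidly improves to Grade 0, then the decision to reinitiate study drug/study regimen will be based upon treating physician's clinical judgment". A completed steroid taper is also required. Without rapid improvement, stop permanently.
- Grade 3 or 4: stop permanently.

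The general considerations at the head of the same guideline name myocarditis as an example when they ask the investigator to "consider whether study drug/study regimen should be permanently discontinued in Grade 2 events with high likelihood for morbidity and/or mortality", where improvement on steroids is not rapid. They do not mention biopsy.

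**Section 7.2.5, Myocarditis.** The management paragraph begins "For patients with suspected myocarditis, investigators should obtain a cardiology consult". It describes management as including "discontinuing drug (permanently if event progresses to Grade 3 or 4". The next paragraph opens: "For rapid recovery of Grade 1 and 2 events, re-expose with treatment is possible". The entry mentions neither biopsy nor the Section 4.3 table.

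**The concern.** The two sections draw the line for a permanent stop in different places. The table has two triggers that are independent of speed of recovery: biopsy proof at any grade, and Grade 3 or 4. Section 7.2.5 has only the second. An investigator who opens the adverse-events section, which is where myocarditis is described as an event of special interest, finds what looks like a complete rule and is not told to look elsewhere.

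What is at stake is whether a patient is given the drug again after an event that the guideline itself groups with those of high morbidity or mortality. A secondary effect is that the recorded reason for stopping, and exposure after the event, would depend on which section the site followed.

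**Working it through.** There is no design figure to reproduce, so the check is a test case followed by a rough count of how often it could arise.

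**Test case: biopsy-proven Grade 2 myocarditis that recovers rapidly to Grade 0.**
1. Any-grade row, Section 4.3: permanent stop. Mandatory.
2. Grade 2 row, Section 4.3: restart at the physician's discretion after the taper. Permissive, and silent on biopsy.
3. Section 7.2.5: re-exposure possible. Permissive, and silent on biopsy, Grade 0 and taper.

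**Steps 1 and 2.** The any-grade row stands above the grade rows and is the more specific condition. Read together, it removes biopsy-proven cases and leaves the Grade 2 discretion for the rest. The rash entry of the same guideline is laid out in the same way: its any-grade cell calls for stopping drug on suspicion of Stevens-Johnson syndrome or toxic epidermal necrolysis, and the grade rows do not repeat this.

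**Steps 1 and 3.** No such layout links these two. Section 7.2.5 gives its own threshold (Grade 3 or 4), and that threshold does not capture the test case. One text forbids what the other allows.

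**Is the test case foreseeable?** Yes. For Grades 2 to 4 the table has Cardiology decide whether and when to take a cardiac biopsy, so a biopsy-proven Grade 2 event is an outcome the plan anticipates. A biopsy-proven Grade 1 event is harder to place, because the table's Grade 1 row covers events without definitive findings.

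**Does a cross-reference settle it?** No. Most neighbouring entries in Section 7.2.5 (pneumonitis, hepatic, gastrointestinal, endocrine, pancreatic, neurological, myositis, renal, skin) send the reader to Table 1 or to the Toxicity Management Guidelines. The myocarditis entry does not.

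**Frequency.** Inputs: 1 myocarditis report in the combination pool and 4 in studies outside it (Section 7.2.5, Myocarditis); a combination pool of 1088 (intestinal perforation and pancreatic entries of Section 7.2.5); planned enrolment of 30 + 20 = 50 (Study Summary), or 35 + 20 = 55 with the upper figure in Section 10.2. Assumption: the myocarditis report comes from that pool of 1088.
- Expected cases of any grade = planned patients × reports / pool size.
- Low: 50 × 1/1088 = 0.046.
- High: 55 × 5/1088 = 0.25. This counts all five reports but adds nothing to the denominator for the outside studies, so it overstates the rate.

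Biopsy-proven Grade 2 with rapid recovery is a subset of these. The documents give no figures from which to size that subset.

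**The case against.** The strongest reply is that Section 4.3 is the dose-modification section and Section 7 deals with monitoring, definitions and reporting, so a careful reader would let the table govern. Section 4.3 says doses are held according to its table, and Section 7.2.5.11 treats the dose-modification guidelines as the base to which general guidance is added. On this view Section 7.2.5 concerns suspected disease, uses permissive wording, and merely fails to repeat an exception found elsewhere.

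Part of this stands. Section 7.2.5 permits re-exposure and does not instruct it. A reader might infer that the protocol gives opposite instructions for the same patient, or that the table contradicts itself between its any-grade and Grade 2 rows. The documents support neither: one text is a requirement and the other a permission, and the table's rows can be read together.

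The rest does not close the gap. Neither Section 4.3 nor Section 7.2.5.11 says which text prevails where they differ. The word suspected marks when the work-up starts; the sentence on re-exposure is in a separate paragraph, speaks of Grade 1 and 2 events without that limit, and follows a sentence that already covers events progressing to Grade 3 or 4.

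A reader might also take the fatal cases in Section 7.2.5 as showing how often the combination causes fatal myocarditis. They cannot carry that weight: one death was judged unrelated by the investigator, and the other patient was also receiving etoposide and carboplatin.

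**Conclusion.** The inconsistency is real but narrow. Section 7.2.5 and the any-grade row of the Section 4.3 table are incompatible for biopsy-proven immune-mediated myocarditis below Grade 3, chiefly Grade 2 with rapid recovery. Section 7.2.5 also lacks the Grade 0 and completed-taper conditions of the Grade 2 row.

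Its reach is small: between about 0.05 and 0.25 expected myocarditis cases of any grade at full planned enrolment, on the pool-size assumption above. The Amendment 12 entry in Appendix E records that the study closed on 7.20.2020 for low accrual, so actual exposure may be lower. The documents do not say whether anyone was still on treatment or re-treatment. Response rate, PFS, OS, sample size and error rates are unaffected, and any effect on discontinuation counts would be negligible.

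Drift between amendments is the likely cause, though this is an inference from Appendix E. Myocarditis entered Section 7.2.5 with Amendment 9. Amendment 10 then updated the cardiac guidance in Section 4.3, and Amendment 11 replaced the guideline, and neither lists a change to Section 7.2.5. The point merits correction because the consequence for a single patient could be serious, not because many patients would meet it.

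**What to change.** Reconcile the Section 7.2.5 myocarditis entry with the any-grade and Grade 2 rows of Section 4.3, so that the handling of biopsy-proven cases is stated once. In Section 7.2.5, replace the free-standing rule on stopping and re-exposure with a reference to the Section 4.3 myocarditis guideline. Name the guideline and section in that reference: Table 1, which other Section 7.2.5 entries cite, is the caption of the contraception list in Section 4.5.1. A short clause in the table saying that the any-grade row governs the grade rows would make the intended reading explicit, if that is the intention. Which clinical rule should apply is for the sponsor to decide.

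The cost is about two sentences of protocol text and, if any patient remains on treatment or re-treatment, a short memo to the site. No data collection or analysis changes.
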